## 6.4 Per-Protocol Analysis Set (PPS)

All subjects from Safety Set without any important protocol deviations. Important protocol deviations are a subset of protocol deviations that may significantly impact the completeness, accuracy, and/or reliability of key study data or that may significantly affect a subject's rights, safety, or well-being. Important protocol deviations will be assigned in a blinded manner prior to database lock. The PPS will be used for sensitivity analysis for the primary efficacy analyses and the non-inferiority analyses.

## 6.5 Other Sets Defined for Tables and Listings

For the purposes of tables and listings the following set is defined:

- Enrolled Set: all subjects who provided informed consent for the study.

# 7 General Considerations for Statistical Analysis

## 7.1 Statistical Significance

All tests of superiority hypotheses will be two-sided and conducted at the 0.05 significance level, and all confidence intervals will be two-sided at the 95% confidence level.

The assessment of non-inferiority will be based on the 2.5% level of significance (using one-sided 97.5% confidence intervals) with a non-inferiority margin of -10%.

## 7.2 Multiplicity

### 7.2.1 Multiplicity Adjustment for Testing of Multiple Hypotheses

A closed testing procedure will be used to control the overall type I error rate at less than 5% across the primary and key secondary variables.

[figure not shown]
The hypothesis testing will start with the primary efficacy objective, then the secondary efficacy objectives (objectives 1 to 4) will be tested, in the order listed in the study objectives (refer to Section 3.2) and shown in the figure below, until a null hypothesis is not rejected (a p-value  $>0.05$  is observed for superiority assessment, or lower limit of the two-sided 95% CI  $\leq -10\%$  for the non-inferiority assessment).

At each step of the procedure, no confirmatory claims will be made unless the objectives are met in all the preceding steps. If the two-sided p-values is larger than 0.05 for any of the superiority tests or the lower limit of the two-sided 95% CI is less than or equal to -10% for the non-inferiority test, then the p-values corresponding to the subsequent tests will be considered as exploratory only.

For all other efficacy and safety analyses, no multiplicity adjustment will be made.

**Figure: Statistical Testing of Rate of Treatment Success in the READY-1 Trial**

Treatment success is defined as restoration of CVAD functionality measured as the ability to withdraw 3 mL of blood and infuse 5 mL of saline.

*Notes:*

1. All tests are performed at the 2-sided  $\alpha=0.05$  level of significance.
2. For tests at 60 and 90 minutes, the rate of treatment success is assessed as the percentage of subjects achieving treatment success following a single instillation of study drug and a dwell time up to 60 or 90 minutes, respectively.
3. For the test at 180 minutes, the rate of treatment success is assessed as the percentage of subjects achieving treatment success following up to two instillations of study drug and a dwell time up to 180 minutes, respectively.

**7.2.2 Multiplicity Adjustment Not Planned for Interim Analysis Futility Analysis**

Of note, the interim analysis will not be conducted as a result of the early stopping of the study. The below text in this section is maintained for consistency with the protocol and to maintain a record of the original plan. See Section 12 for additional details.

No multiplicity adjustment will be incorporated for the separate interim futility analysis to assess the conditional power for the non-inferiority test of CUSA-081 compared to alteplase in the rate of treatment success following a single administration of study drug with a dwell time up to 90 minutes (the second step in the closed testing procedure). Of note, there will be no stopping of any arm for efficacy and no claims of efficacy made on the basis of the futility analysis. The recommendation of a threshold to stop the study for futility will be considered as “nonbinding,” meaning the futility stopping criteria are guidelines to the DMC that may or may not be followed, depending on the totality of the available interim results.

### 7.3 Handling of Missing Data

In general, except as described below, missing data will not be imputed.

The number of subjects with missing data will be presented under a “Missing” category. Unless otherwise stated, missing values will not be included in the denominator count when calculating percentages.

When quantitative variables are being summarized, only the non-missing values will be evaluated for calculating summary statistics.

Other critical missing data, if any, will be discussed during the blind review of the data. Decisions will be fully documented in the Data Review Report.

Treatment Success: Missing CVAD Assessment

By design, all subjects exit the treatment algorithm once patency is achieved and no further assessments of catheter clearance are performed. Subjects are considered a treatment success at the time point at which patency was achieved and also at all subsequent time points during the treatment period.
 
Otherwise, if missing data is observed for assessment of treatment success and patency was not achieved prior to the time point with missing data, then the subject will be considered as a failure (worst case scenario) at the time point with missing data. The summary statistics for treatment success will display the derived data, including imputation for any missing data observed prior to treatment success.

Medications: Missing/Incomplete Date

In case of missing or incomplete dates/times not directly allowing allocation to any category of medications, a worst-case allocation will be done according to the available parts of the start and the stop dates/times. The medications will be allocated to the first category allowed by the available data, according to the following order:
 

1. Concomitant medication;

2. Maintained medication;

3. Post-treatment medication;

4. Prior medication.

Procedures: Missing/Incomplete Date

In case of missing or incomplete dates/times not directly allowing allocation to any category of procedure, a worst-case allocation will be done according to the available parts of the start and the stop dates/times. The procedure will be allocated to the first category allowed by the available data, according to the following order:
 

1. Concomitant procedure;

2. Maintained procedure;

3. Post-treatment procedure;

4. Prior procedure.

**Adverse Events (AEs): Missing/Incomplete Date**

In case of missing or incomplete date/time not directly allowing allocation to any of the category of AEs, a worst-case allocation will be done according to the available parts of the start and the stop dates/times. The AE will be allocated to the first category allowed by the available data, according to the following order:

1. Treatment emergent;
2. Post-treatment;
3. Pre-treatment.

**Adverse Events (AEs): Missing Severity**

In case of missing severity, the severity will not be imputed and will be reported as “Missing”. For the table of TEAEs by maximum severity, the maximum severity will be considered as the maximum of the non-missing severities for the relevant subject and preferred term.

## 7.4 Covariates

No covariate adjustment analysis will be performed in any of the efficacy analysis.

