## 5 Sample Size

For the primary assessment of the superiority of CUSA-081 vs. placebo, a sample size of 450 in the active arm (CUSA-081), and 50 in the control arm (placebo), will provide >99% power to detect a difference of  $\geq 35\%$  using a two-sided test at significance level of 0.05. The expected placebo response rate is approximately 20%.

For the assessment of the non-inferiority of CUSA-081 vs alteplase, a sample size of 450 in the active arm (CUSA-081), and 300 in the control arm (alteplase) will provide 87% power at the 2.5% significance level (that is by using one-sided 97.5% confidence intervals (CI)) with a non-inferiority margin of -10%, assuming an equal response rate of 75% in the control arm (alteplase), and the active (CUSA-081) arm. A sample size of 450 in the active arm (CUSA-081), and 300 in the control arm (alteplase) will also provide 92% power to detect a difference of 10% between the success rates using a two-sided test at significance level of 0.05.

A minimum of 841 subjects will be randomized in order to achieve a minimum of 800 subjects completing the study.

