**8.2.2 CVAD History**

Time between Screening CVAD assessment and first drug administration (hours), CVAD type, CVAD lumen, number of lumens, indications for CVAD insertion, duration of CVAD dysfunctional (hours) and when and by whom the CVAD was identified as dysfunctional (Patient/caregiver identified, Healthcare provider not at study site, Healthcare provider at study site) recorded at Screening Visit will be presented by treatment group and overall using the FAS. Summaries will be repeated using the Safety, ITT and PP Sets.

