### Non-Inferiority Hypotheses

The hypotheses for the non-inferiority are as follows:

The null hypothesis H0:  $R_c - R_a \leq -10$   
The alternative hypothesis H1:  $R_c - R_a > -10$

Where Rc=Rate of success of CUSA-081  
Ra=Rate of success of alteplase

Assessment of non-inferiority will be based on the 95% confidence interval for the difference in the rate of treatment success between CUSA-081 vs alteplase following a single administration with a dwell time up to 90 minutes.

Non-inferiority will be demonstrated (or null hypothesis will be rejected) when the lower limit of the 95% confidence interval for the difference in rate of success is greater than -10% (See Section 14.1).

The number and percent of subjects with treatment success by treatment group and time point will be summarized. The rate difference and associated 95% Wald confidence intervals between CUSA-081 and placebo or alteplase will be estimated. The between treatment comparisons will be performed using a 2-sample z test for proportions.

For superiority hypotheses, the primary analysis will be the analysis performed on the FAS. Analyses will be repeated based on the ITT and PP Sets as sensitivity analyses. For non-inferiority hypotheses, the analysis based on the PP Set will be considered as the primary analysis.

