### **Sensitivity Analysis**

A sensitivity analysis will be performed on the primary efficacy endpoint using a logistic regression model with age (<18, ≥18-<65, ≥65-<85, ≥85 years) and region (US vs Non-US) as factors. The odds-ratio, 95% confidence interval for the odds-ratio and the p-value will be displayed for each treatment group comparison (See Section 14.4).

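### SAP 7.4 rules out all covariate adjustment while 9.1 plans an adjusted model on the odds-ratio scale; an adjusted risk difference for the alteplase comparison would be a cheap, modest improvement

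*SAP*

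**What the plan says.** SAP 7.4 consists of one sentence: "No covariate adjustment analysis will be performed in any of the efficacy analysis". It makes no exception for sensitivity analyses.

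SAP 9.1, under its Sensitivity Analysis heading, says: "A sensitivity analysis will be performed on the primary efficacy endpoint using a logistic regression model with age" in four categories, plus US versus non-US region. The output is an odds ratio with its confidence interval and p-value. SAP 14.4 gives the code. SAP 16.1 lists the tables on the FAS, ITT and PPS (14.2.1.5.1-3, and 14.2.2.5.1-3 for 120-180 minutes), with CUSA-081 versus alteplase among the comparisons. SAP 9.3.1 and protocol 12.3.5 also leave room for exploratory covariate analyses.

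Non-inferiority is decided on another scale. SAP 7.1 sets the "2.5% level of significance (using one-sided 97.5% confidence intervals) with a non-inferiority margin of -10" (percent), and SAP 9.1 requires that the "lower limit of the 95% confidence interval for the difference in rate of success is greater than -10" (percent). The interval is the unadjusted Wald interval, and the PPS is the primary set for this test.

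Among the screening data that SAP 8.2.2 summarises are "CVAD type, CVAD lumen, number of lumens, indications for CVAD insertion, duration of CVAD dysfunctional (hours"). SAP 7.6 uses CVAD type, number of lumens and duration of dysfunction (0-5 h, >5-48 h) as subgroup factors. None of them enters the logistic model. SAP section 2 describes block randomisation and states no stratification factor.

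**The concern.** Two things look wrong on the page. First, 7.4 and 9.1 cannot both be followed as written: a programmer who obeys 7.4 would not produce tables that 16.1 requires. Second, the only adjusted analysis cannot speak to the first secondary objective. It gives an odds ratio where the margin is a difference in percentages, and it ignores the baseline catheter data.

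What may be at stake is precision in the comparison with the least spare power. Among the planned powers, non-inferiority to alteplase has 87%, against more than 99% for superiority over placebo and 92% for a 10-point difference from alteplase. The study was also stopped early (SAP section 12), so the realised power may be lower. Adjusting for baseline variables that predict outcome narrows the interval for the risk difference without new data.

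**Working it through.** **Inputs.** SAP section 5: "a sample size of 450 in the active arm (CUSA-081), and 300 in the control arm (alteplase) will provide 87% power", "assuming an equal response rate of 75% in the control arm (alteplase), and the active (CUSA-081) arm". Margin -10 points and one-sided 0.025 (SAP 7.1). Alteplase success at 90 minutes, interpolated: 67.3% (SAP 5.1, Table 3). The prognostic strength of the catheter variables is not given anywhere, so it is varied as an assumption.

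**The plan's own figure.** With a true difference of zero, SE = sqrt[p(1-p)(1/450 + 1/300)] and power = Phi(0.10/SE - 1.96).

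- At p = 0.75: SE = sqrt(0.1875 x 0.005556) = 0.03227, so power = Phi(3.098 - 1.96) = 87.3%. The stated 87% reproduces, so the trial was sized for the unadjusted test.
- At p = 0.673: SE = sqrt(0.2201 x 0.005556) = 0.03497, so power = Phi(2.860 - 1.96) = 81.6%.

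**With adjustment.** If baseline covariates explain a share v of the outcome variance, a standardised risk difference has approximately SE x sqrt(1 - v) in large samples.

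| v | Power, p = 75% | Power, p = 67.3% |
|---|---|---|
| 0 | 87.3% | 81.6% |
| 3% | 88.2% | 82.7% |
| 5% | 88.9% | 83.5% |
| 10% | 90.4% | 85.4% |

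At p = 75%, the 95% half-width is 6.33 points at v = 0, 6.17 at 5% and 6.00 at 10%.

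**What v might be.** These success rates are illustrative and do not come from the documents.

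- A 50/50 covariate with 57% and 77% success gives v = 0.25 x 0.20^2 / (0.67 x 0.33) = 4.5%.
- Three equal groups at 57%, 67% and 78% give a between-group variance of 0.00736; divided by 0.673 x 0.327 = 0.220, v = 3.3%.
- A 50/50 covariate with 70% and 80% success gives only 1.3%.

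A range of 3-5% is therefore reasonable if the variables matter moderately. The 10% row needs a stronger predictor, for example 60% versus 90% success (12%).

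**Simulation check.** A post-stratified risk difference was simulated at 450/300, with 10,000 trials per setting. With strata at 65% and 85%, power was 87.8% unadjusted and 89.3% adjusted. With strata at 60% and 90%, it was 87.9% and 91.7%. At a true difference of -10 points, the one-sided error was 2.3-2.6% for both methods.

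**Early stopping.** The achieved sample size is not stated. At an assumed 52% of plan (416 of 800, the planned interim fraction) and p = 75%, power would be 60.8% unadjusted, 63.0% at v = 5% and 65.4% at v = 10%.

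**The scale problem.** A 10-point deficit corresponds to a different odds ratio at each alteplase rate:

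- 67.3%: (0.573/0.427)/(0.673/0.327) = 0.652
- 75%: (0.65/0.35)/(0.75/0.25) = 0.619
- 85%: (0.75/0.25)/(0.85/0.15) = 0.529

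Conversely, an odds ratio of 0.619 means -11.3 points at 67.3% and -7.2 points at 85%. No single odds-ratio bound represents the margin. The modelled odds ratio is also conditional on age and region, so it is not the quantity the margin was set for.

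**The case against.** The strongest reply is that the unadjusted analysis is sound. Protocol 12.3.4 specifies it, the stated power rests on it, it omits no stated stratification factor, and its interval already allows for chance imbalance. All of that stands. A reader might infer from the concern that the non-inferiority test is flawed or loses known precision. The documents do not support this: no section says that CVAD type or duration of dysfunction predicts success, and listing them as subgroups does not show that they do.

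A reader might also infer that the SAP means the odds ratio to serve as a non-inferiority test. It does not. Section 9.1 calls the model a sensitivity analysis of the primary endpoint, and the CUSA-081 versus alteplase odds ratio can support the superiority objective. The valid point is narrower: no adjusted analysis is specified for the non-inferiority question.

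The gain is also small. The two moderate illustrations above (3.3% and 4.5%) imply roughly 1 to 1.7 power points, and at half the planned size adjustment would not rescue the test.

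Finally, SAP section 12 says that the analysis after early closure will be exactly the one planned for the end of the study, so a new deciding estimator would be a departure. This is a fair constraint, but it can be met: the same section already records a change of primary analysis set for this very test. What the reply leaves untouched is the conflict between 7.4 and 9.1.

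**Conclusion.** The contradiction between SAP 7.4 and SAP 9.1/14.4 is plain and should be removed. The planned adjusted model cannot inform the -10 point margin, because it reports odds ratios only, and it uses none of the collected catheter variables.

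The rest is a low-cost efficiency improvement and not the correction of an error. At the planned 450/300, a variance reduction of 3-5% is worth about 1 to 2 power points: 0.9 to 1.6 at a 75% success rate and 1.1 to 1.9 at 67.3%. This rests on three assumptions: that the covariates are prognostic to that degree, that the two success rates are equal, and that the full planned numbers are analysed. If the covariates are not prognostic, there is no gain. The power gain is realised only if the adjusted interval is the one that decides; otherwise the adjusted result is supporting evidence.

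**What to change.** Before unblinding:

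1. Reword 7.4 to say which efficacy tests are unadjusted and to name the adjusted analyses in 9.1 and 14.4.
2. Add to 9.1 text such as:

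> For CUSA-081 versus alteplase at 90 minutes, the difference in success rates will also be estimated by standardisation (g-computation) from a logistic model with treatment, CVAD type, duration of dysfunction (0-5 h, >5-48 h), age category and region, with a delta-method 95% confidence interval. It will be computed on the PPS (primary for non-inferiority) and on the FAS.

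3. Drop the under-18 age level from the model. Eligibility starts at 18, so it should be empty.
4. Give rules for missing covariates and for CVAD type recorded as Other. SAP 7.6 leaves Other out of the subgroup analyses; copying that into the model would drop subjects from the comparison. One option is to keep Other as its own level, merged into the most frequent type if sparse, and to assign missing values to the most frequent category.
5. State in advance whether the adjusted or the unadjusted interval decides non-inferiority, and report the other alongside. If the adjusted interval decides, list it in SAP section 12 as a change from protocol 12.3.4.

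The cost is SAP wording, a few lines of code and slightly more output, with no new data. If the adjusted interval is made decisive, there is also a documented departure from the protocol's unadjusted method.

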## 7.5 Interim Analyses

Of note, the interim analysis will not be conducted as a result of the early stopping of the study. The below text in this section is maintained for consistency with the protocol and to maintain a record of the original plan. See Section 12 for additional details.

A single interim analysis for futility will be performed to evaluate if the study should be stopped for futility. There will be no stopping rules for efficacy at the time of this interim analysis and no efficacy claims on the basis of the interim analysis. Therefore no statistical adjustment will be done for the final analysis. The futility interim analysis is planned to be performed when approximately 416 patients have completed the study. The timing of the futility interim analysis could be modified based on the progress of the recruitment and planning of other studies.

The futility analysis will assess the conditional power for the test of non-inferiority of CUSA-081 compared to alteplase in the rate of treatment success following a single administration of study drug with a dwell time up to 90 minutes (see Section 14.5 for the calculation details of the condition power).

### Conditional Power

The conditional power,  $CP(d)$ , denotes the conditional power computed as if the observed estimate is the effect size governing the rest of the trial.  $CP(d)$  will be derived based on the following formula [3]:

$$CP(d) = \Phi \left( -\frac{1}{\sqrt{1-I}} \left( z_{\alpha} - \frac{z_I}{\sqrt{I}} \right) \right),$$

where

$\Phi()$  = normal cumulative distribution function

$I$  = information level at time of the interim =  $\frac{n_{I1} + n_{I2}}{N_1 + N_2}$

$n_{I1}$  = number of subjects in CUSA-081 group at interim

$n_{I2}$  = number of subjects in alteplase group at interim

$N_1$  = number of subjects in CUSA-081 group planned at the end of the trial (i.e. 473 subjects)

$N_2$  = number of subjects in alteplase group planned at the end of the trial (i.e. 315 subjects)

$z_\alpha$  = the standard normal critical value for a test with a type I error rate of  $\alpha$  ( $\alpha$  = one-sided 0.025)

$$z_I = \frac{\text{diff}_I - \Delta}{SE_I}$$

$$\text{diff}_I = p_{I1} - p_{I2}$$

$p_{I1}$  = proportion of successes in CUSA-081 group at interim

$p_{I2}$  = proportion of successes in alteplase group at interim

$\Delta$  = non-inferiority margin = -0.1 (based on the non-inferiority hypotheses presented in section 9.1)

$$SE_I = \sqrt{\frac{p_{I1}(1 - p_{I1})}{n_{I1}} + \frac{p_{I2}(1 - p_{I2})}{n_{I2}}}$$

### Number and Timing of Interim Analyses

A single interim analysis will be conducted when approximately 416 subjects have completed the study.

### Statistical Evaluation of Futility

The conditional power for the test of the first secondary objective will be calculated on the basis of the observed data at the time of the interim analysis. The study could be terminated early in case the conditional power at the interim analysis is lower than some pre-defined threshold (“conditional power threshold”).

The exact conditional power threshold will be defined in the DMC charter, to be finalized prior to the interim database lock and prior to any unblinding for the interim analysis. Of note, the futility stopping criteria will be considered as “nonbinding” (i.e., they are guidelines that may or may not be followed, depending on the totality of the available interim results). Aside from potentially halting the study for futility, there will be no additional changes to the study design on the basis of the futility analysis. Specifically, there will be no efficacy stopping rules related to the analysis, nor will there be any changes to the planned arms or allocation to the arms, and no formal hypothesis testing of the named study objectives. For this reason, the futility analysis does not cause inflation of type 1 error and no multiplicity adjustment will be conducted on the basis of the futility analysis.

